8. STATISTICAL HYPOTHESIS AND MULTIPLICITY COMPARISON

In this study, there are multiple comparisons in the primary analysis. The hypothesis test will be performed for the primary efficacy endpoint, i.e., the comparison of 4 mg QD and 8 mg QD groups with placebo, respectively. The type I error of the primary endpoint will be controlled at the level

of 0.1 bilaterally by using the Hochberg incremental procedure¹. The statistical hypotheses are detailed in the efficacy analysis section.

Unless otherwise specified, the significance level for other analyses will also be set to 0.1 bilaterally.

9. DESCRIPTION OF TREATMENT GROUPS

Unless otherwise specified, the statistical description and summary will be presented according to below treatment groups as follows.

Table 4 Description of Treatment Groups

Treatment Description	Final Data Display
4 mg tablet + placebo tablet	4 mg QD SHR0302
4 mg tablet + 4 mg tablet	8 mg QD SHR0302
Active drug total	Treatment Total
Placebo tablets + placebo tablets	Placebo
Total	Total

10. CONSIDERATIONS FOR DATA ANALYSIS AND DATA DEALING CONVENTIONS

10.1 GENERAL RULES FOR STATISTICAL DESCRIPTION

Unless otherwise specified, descriptive statistics appropriate to the type of variable will be provided.

Continuous variables will be presented with the number of non-missing values (n), mean, standard deviation (SD), median, minimum, and maximum values. If less than 3 observations, only n, minimum and maximum values will be presented.

Categorical variables will be presented as frequencies and percentages.

10.2 STATISTICAL RESULT REPORTING RULES

Analyses will be performed using SAS® version 9.4 or higher.

All analysis outcomes will be presented by statistical tables and/or figures. And the original data listings corresponding to the tables or figures will be provided, including important derivation variables and study endpoints, and unscheduled visit data. The general rule for sorting variable in listings is by study site, dose group/treatment group, subject ID, demographic characteristics, visit/treatment cycle, date and time, test/assessment, original results (unit), standard/derived results or study endpoints, explanation for results, reason and other information. The variable sort could be adjusted according to original data, data characteristics or requirement from report. Please refer to the mock shells for each listing, as not all of which will be specified in this analysis plan.

The decimal places are specified as below.

Table 5 Basic Descriptive Statistics

Name	Illustration	Decimal Places (dp)
N	Number of subjects in analysis set	Always present 0 dp
n	Number of non-missing observations	Always present 0 dp
%	Percentage	Categorical data 1 dp

Mean	Arithmetic Mean	1 more dp than original data
SD	Standard Deviation	2 more dp than original data
Median	Median	1 more dp than original data
Min.	Minimum value	Same with original data
Max.	Maximum value	Same with original data

Table 6 Derived Data Or Statistics of Estimated Parameters

名称	说明	小数位数 (dp)
SE	Standard Error	1 more dp than derived data or parameter
95% CI	95% Confidence Interval	1 more dp than derived data or parameter
p value	P value	Present 3 dp, or < 0.001

The derived data and its statistics will be 1 more decimal place than the original data or the corresponding statistics.

Reasonable decimal places will be adjusted for proper presentation and interpretation.

11.DERIVED AND TRANSFORMED DATA

11.1 BASELINE DEFINITION AND CHANGE FROM BASELINE

Unless otherwise specified, the baseline value for a parameter of interest is the latest non-missing value prior to date of the first administration of study drug.

Change from baseline and percentage from baseline will be derived as follows:

- Change from baseline = the post-baseline value - the baseline value of a parameter of interest for a subject.
- Percentage change from baseline = (post-baseline value - the baseline value)/ baseline value of a parameter of interest for a subject.

If either the baseline or the post-baseline value is missing, then the change or percentage change will be set to missing.

11.2 STUDY DAY

Day 1 = Date of the first administration of study drug for a subject

Study Day

= Calendar Date – date of the first administration of study drug + 1 if the calendar date is on or after the date of the first administration of study drug, or

= Calendar Date - date of the first administration of study drug if the calendar date is before the first administration of study drug

11.3 MULTIPLE MEASUREMENTS AT THE SAME TIMEPOINT

If there are multiple measurement results at a timepoint, unless otherwise specified, use the mean of these measurements to summarize and derive. If there is unscheduled measurement, consider the

scheduled data firstly, if missing at the scheduled visit, then impute with closest non-missing per-protocol data within the visit window to make analysis.

11.4 EARLY WITHDRAWA

All subjects who early withdraw/discontinue study drug administration will be documented, and the reasons will also be recorded in the final clinical study report. All available data will be included in each applicable analysis set for summarization and analysis. The definition of each analysis set is detailed in Section 7.

If the study is terminated early, all available data will be listed and the study team will review these data to evaluate which statistical analysis will be still applicable.

11.5 MISSING DATA

In general, missing data will not be included in descriptive statistics analysis.

Missing efficacy data will be handled as specified in section of efficacy analysis.

For safety data, if there is “ $< x$ ”, “ $\leq x$ ”, “ $> x$ ”, or “ $\geq x$ ” value in the quantitative safety data, the “ x ” will be used for derivation or summary. But the final handling and analysis will be based on medical opinion.

If the dates used for derivation or calculation are not complete or missing, the following rules will be considered.

- If the onset date of an AE is missing or incomplete, it is assumed to have occurred during the study treatment phase, except if the stop date indicates that the event happened before the study treatment.
- If the phase of a concomitant medication used cannot be identified, due to missing or incomplete onset/end date, it will be assumed to have occurred during both screening and study treatment phase, except if partial dates indicate that the medication is not administrated in one of the study phases.
- When calculating the age of subject, if birth date is missing or not complete, the age collected in CRF will be used, else impute with the first date of the month or the first day (01January) of the year.

12. DATA SOURCE

Detailed sources of all types of data that will be analyzed in this SAP are described as below.

Table 7 Data source

Data type	Origin	Data format	Responsible Party
Subject Demographics, Baseline Characteristics, Efficacy, Safety	eCRF	The SAS dataset (. sas7dat)	[REDACTED]

13. STUDY POPULATION ANALYSIS

13.1 DISPOSITION OF SUBJECTS

In all screened subjects, the number and percentage of subjects screened, screen failure, screened successfully and randomized, screened successfully and but not randomized will be summarized as well as the reasons.

In all enrolled subjects, the number and percentage will be summarized of subjects enrolled, randomized, with at least one dose of assigned drug, with week 12 remote visit, with week 12 prolonged visit and those who have completed study or discontinue from treatment or study along with reasons. The flow chart of subject disposition will be provided in a separate file.

The number of subjects in different analysis sets by treatment group will be summarized in enrolled subjects.

13.2 PROTOCOL VIOLATION

Major protocol deviations (including informed consent deviations, deviation of inclusion/exclusion criteria, deviation of termination/withdrawal criteria, study medication deviation, use of prohibited medications, trial procedures/procedures, and any other deviation deemed likely to have a significant impact on study results) will be summarized.

All major protocol deviations will be discussed and identified at the data review meeting and the impact on each analysis set will be assessed.

13.3 DEMOGRAPHIC AND BASELINE CHARACTERISTICS

The following demographic and baseline characteristic will be summarized. Continuous variables will use statistics including mean, standard deviation and so on, Number of non-missing values (n) and corresponding percentage (%) will be presented for descriptive presentation of categorical data.

- Continuous variables: age, height, weight, body mass index (BMI)
- Categorical variables: gender, ethnic group, race

Age = INT((date of informed consent - date of birth)/365.25);

Body mass index (BMI) = weight (kg)/height (m²).

Baseline characteristics includes tobacco use (summary of smoking status and frequency. Smoking status includes never smoke, previous smoke and current smoke), alcohol use (summary of use status and frequency. Use status includes never use, previous use and current use), virology test (hepatitis B surface antigen, hepatitis C antibody, human immunodeficiency virus antibody), tuberculosis infection test (summary of both tests types and results), and primary diagnosis of atopic dermatitis (disease duration), atopic dermatitis disease activity (Eczema Area and Severity Index (EASI), BSA, Investigator's Global Assessment (IGA) and Pruritus Numerical Rating Scale (NRS). Atopic dermatitis disease activity will be summarized using baseline results.

Duration of atopic dermatitis = (date of initial dose of IMP – date of diagnosis of atopic dermatitis + 1)/365.25 in years. When the date of primary diagnosis for atopic dermatitis recorded in the eCRF is incomplete or missing, the following rules will be applied for imputation:

- If day is missing then 15th of the current month will be imputed, and if month is missing then July of the current year will be imputed;
- If duration of atopic dermatitis is less than 1 year due to the imputation, then 1st day will be used for missing days, and January will be used for missing months;
- Missing year will not be imputed;
- Listings of missing dates will be presented as collected on the eCRF.

Baseline results for other safety endpoints will be summarized in safety analysis part. Other efficacy endpoints will be summarized in the efficacy analysis part.

13.4 MEDICAL HISTORY

Medical history and concomitant illness will be presented for the safety analysis set.

Medical history and concomitant illness will be coded using Medical Dictionary for Regulatory Activities (MedDRA) and summarized by system organ class (SOC) and preferred term (PT).

Medical history is defined as those conditions ended prior to the date of the first administration of study drug; concomitant illness is defined as those conditions started prior to and ended on or after the date of the first administration of study drug. If end date of one condition could not show earlier than date of the first administration of study drug then it will be classified into concomitant illness.

13.6 PRIOR AND CONCOMITANT MEDICATIONS/NON-DRUG TREATMENTS

Prior and concomitant medication and non-drug treatment data are captured in the CRF. Prior and concomitant medications will be coded by WHODD and summarized by anatomical therapeutic chemical (ATC) classification system and preferred name (PN). Prior and concomitant non-drug treatment will be coded by MedDRA and summarized by system organ class (SOC) and preferred term (PT) respectively.

The definition of prior and concomitant medications/non-drug treatments are the same as prior and concomitant medications/non-drug treatments for atopic dermatitis.

14.EFFICACY ANALYSIS

14.1 OVERVIEW OF EFFICACY ANALYSES

The following hypotheses will be tested based on the primary endpoint and objective:

- H_{01} : Percentage of subjects achieving an IGA response in the SHR0302 8 mg QD dose group at Week 12 - Percentage of subjects achieving an IGA response in the placebo group at Week12 = 0;
- H_{11} : Percentage of subjects achieving an IGA response at Week 12 in the SHR0302 8 mg QD dose group - Percentage of subjects achieving an IGA response at Week 12 in the placebo group $\neq 0$.
- H_{02} : Percentage of subjects achieving an IGA response in the SHR0302 4 mg QD dose group at Week 12 - Percentage of subjects achieving an IGA response in the placebo group at Week12 = 0;
- H_{12} : Percentage of subjects achieving an IGA response at Week 12 in the SHR0302 4 mg QD dose group - Percentage of subjects achieving an IGA response at Week 12 in the placebo group $\neq 0$.

By using the Hochberg¹ incremental procedure, the type I error for the primary endpoint will be controlled at the level of 0.1 bilaterally. Two p-values will be gained and sorted ($p_{(2)} \geq p_{(1)}$). Then start with the least significant comparison ($p_{(2)}$) and continue as long as the test is not significant until the first time when a significant comparison occurs, and all remaining hypotheses will be rejected. The decision rules are provided in below figure 2.

[figure not shown]

Figure 2 The decision rules of hypothesis

NOTE: $H_{(01)}$ is the corresponding null hypothesis of the smallest p value $p(1)$

Analyses of secondary efficacy and other analyses will be provided for comparison 4 mg QD and 8 mg QD versus placebo, respectively.

14.2 PRIMARY EFFICACY ANALYSIS

Analysis of the primary efficacy endpoint will be based on FAS.

The primary efficacy endpoint for this study is the percentage of subjects achieving IGA response at Week 12. IGA is the investigator's global assessment of the subject's general condition and consists of a 6-point severity scale from clear to very severe disease ("complete clearance", "almost

complete clearance", "mild", "moderate", "severe", and "very severe"). IGA response is defined as IGA score of 0/1 (complete or almost complete clearance of skin lesions) with an improvement in IGA score by ≥ 2 from baseline.

Subjects who early withdraw from the study for any reason will be considered as non-responders at each post-withdrawal assessment time point. Descriptive summaries of the primary efficacy endpoint will be based on non-missing data only.

Due to the impact of the COVID-2019 pandemic, subjects may have their primary efficacy endpoint assessed outside the scheduled time window of visit 6. If the primary efficacy endpoint is missing within the planned time window (between study days 82 and 88), it will be considered to impute with results of assessment within 89 to 102 study day (ie, extended visit).

The method of normal approximation to binomial will be used to test whether each active drug group is superior to the placebo group. Estimation of the difference and its 90% confidence interval between each drug group and the placebo group, as well as the corresponding p value for test will be provided.

Referenced SAS code:

```
PROC FREQ DATA = adam.adeff;  
  TABLE treat*aval/CHISQ RISKDIFF (CL = WALD) ALPHA = 0.1;  
  RUN;
```

In the above codes, variables are defined as follows:

Aval = IGA response at Week12

Treat = treatment group

In addition, IGA response and its 90% confidence interval at Week 12 will also be provided for each treatment group.

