9.1 Sample Size Determination and Hypothesis

This study is planned to enroll 132 subjects, 44 in each group (assuming 9% dropout rate, 120 completers, 40 completers in each group), and provide approximately 81% power to detect 20% difference in the primary endpoint between SHR0302 and placebo assuming placebo response rate is approximately 10% and response rates of SHR0302 4 mg QD, 8 mg QD are around 30%. By using the Hochberg incremental procedure, the type I error for the primary endpoint was controlled at a level of 0.1 bilaterally.

The null and alternative hypotheses to be tested are:

 H01: Percentage of subjects achieving an IGA response in the SHR0302 8 mg QD dose group at Week 12 - Percentage of subjects achieving an IGA response in the placebo group at Week 12 = 0;

- H11: Percentage of subjects achieving an IGA response at Week 12 in the SHR0302 8 mg QD dose group Percentage of subjects achieving an IGA response at Week 12 in the placebo group $\neq 0$.
- H02: Percentage of subjects achieving IGA response in the SHR0302 4 mg QD dose group at Week 12 Percentage of subjects achieving IGA response in the placebo group at Week 12 = 0;

H12: SHR0302 Percentage of Subjects Achieving IGA Response at Week 12 in the 4 mg QD Dose Group - Percentage of Subjects Achieving IGA Response at Week 12 in the Placebo Group $\neq 0$.

Two p-values will be gained and start with the least significant comparison and continue as long as tests are not significant until the first time when a significant comparison occurs, and all remaining hypotheses will be rejected. Order the two p values as (p(2), p(1)), where $p(2) \ge p(1)$. The decision rules are provided in below figure (Figure 2).

[figure not shown]

Figure 2. The decision rules of hypothesis

NOTE: H(01) is the corresponding null hypothesis of the smallest p value p(1)

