6. SAMPLE SIZE CONSIDERATIONS

This study is planned to enroll 105 subjects, 35 in each group, and provide approximately 82% power to test differences in primary endpoint between at least one active group and the placebo group, assuming the response rates in the 4 mg QD group, the 8 mg QD group and the placebo group are 26%, 26%, and 6%, respectively. By using the Hochberg incremental procedure, the type I error for the primary endpoint is controlled at the level of 0.1 bilaterally.

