14.4 SENSITIVITY ANALYSES

14.4.1 Statistical analysis methods

The primary efficacy endpoint of IGA response at Week 12 specified in Section 14.2 will be tested based on the full analysis set (FAS) using Fisher's exact test together with Exact Unconditional 90% confidence interval of difference between active groups versus placebo group. The 90% confidence interval of IGA response rate at Week 12 based on Clopper-Pearson method will also be reported for each treatment group.

Referenced SAS code:

```
PROC FREQ DATA = adam.adeff;  
  TABLE treat*aval/CHISQ RISKDIFF ALPHA = 0.1;  
  EXACT RISKDIFF (METHOD = SCORE);  
  RUN;
```

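### The primary 90% interval for each active-minus-placebo difference is Wald, which slightly under-covers at the planned rates; a Newcombe interval and a named per-arm method would be a cheap improvement

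*SAP*

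**What the plan says.** Section 14.2 of the SAP tests each active dose against placebo by the normal approximation to the binomial and reports the difference with a 90% interval. The reference code is "TABLE treat*aval/CHISQ RISKDIFF (CL = WALD) ALPHA = 0.1", which fixes the interval for the difference as Wald. After the code comes a second promise: "In addition, IGA response and its 90% confidence interval at Week 12 will also be provided for each treatment group". No method is attached to that per-arm interval.

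Section 14.4.1 plans a sensitivity analysis of the same endpoint in the full analysis set. It uses Fisher's exact test, an exact unconditional 90% interval for the difference, and per-arm exact intervals: "The 90% confidence interval of IGA response rate at Week 12 based on Clopper-Pearson method will also be reported". Table 8 lists the exact test as sensitivity analysis 2.

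Section 14.3 keeps the normal approximation for secondary binary endpoints only when expected responders and non-responders are both at least 5 in each group, and otherwise moves to Fisher's exact method. Section 14.2 has no such rule.

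The planning assumptions are in SAP section 6: "This study is planned to enroll 105 subjects, 35 in each group", with rates such that the two active groups and "the placebo group are 26%, 26%, and 6%, respectively".

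**The concern.** The Wald interval estimates its variance by plugging in the observed proportions. When one proportion is near zero and the arm is small, that estimate is often too small and the interval too narrow. Here the expected number of placebo responders is about two. The SAP treats expected counts below 5 as a reason to leave the normal approximation for secondary endpoints, yet it leaves the primary endpoint on it. At stake is the precision attached to the trial's main effect estimate: an interval labelled 90% that covers less often than that. The unnamed per-arm method matters because, if Wald were chosen, the placebo interval could be badly behaved.

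**Working it through.** **Inputs.** SAP section 6: 35 per arm; 26%, 26% and 6%; two-sided 0.10 with Hochberg over two comparisons. SAP section 14.2: Wald, 90%, so z = 1.645. Protocol section 9.1, for comparison: "assuming placebo response rate is approximately 10" per cent, 30% on active, 44 randomised and 40 completers per arm.

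**The plan's own figure.** The SAP says the design will "provide approximately 82% power to test differences in primary endpoint between at least one active group and the placebo group". A simulation of 1,000,000 trials with a shared placebo arm and Hochberg (reject both if the larger p is at most 0.10, otherwise reject the smaller if it is at most 0.05) gives 82.7% with pooled variance and 84.4% unpooled. The stated power reproduces, so the inputs are read as intended.

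**Expected count.** 35 x 0.06 = 2.1 placebo responders. If expected counts are instead pooled over the two arms, the figure is 35 x (0.26 + 0.06)/2 = 5.6. That just passes the section 14.3 threshold, but there is a 29% chance that the observed total falls below the 10 responders needed.

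**Difference interval.** Wald is d ± 1.645 × sqrt[p1(1−p1)/n + p0(1−p0)/n]. At the planned rates this is 0.20 ± 1.645 × sqrt[(0.1924 + 0.0564)/35] = 0.20 ± 0.139, or 6.1% to 33.9%. Coverage is the sum of the binomial probabilities of all pairs of counts whose interval contains the true difference:

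| n per arm | Active / placebo | Source of rates | Wald | Newcombe |
|---|---|---|---|---|
| 35 | 26% / 6% | SAP | 88.6% | 90.4% |
| 40 | 30% / 10% | Protocol | 89.3% | 90.0% |
| 44 | 30% / 10% | Protocol | 89.0% | 90.4% |
| 35 | 20% / 3% | assumed | 87.4% | 91.2% |
| 35 | 15% / 2% | assumed | 85.5% | 92.4% |

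With placebo held at 6% and the active rate scanned from 6% to 50%, Wald coverage runs from 86.4% to 89.7%. At 26% / 6% the Wald errors are 5.4% (lower limit above the truth) and 6.0% (upper limit below it), against 5% nominal each. At 15% / 2% they are 3.8% and 10.7%.

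**No placebo responders.** The probability at 6% is 0.94^35 = 11.5%. The placebo variance term vanishes and the active term stays. For 9/35 against 0/35, Wald is 0.257 ± 1.645 × sqrt(0.257 × 0.743/35) = 13.6% to 37.9%; Newcombe is 13.3% to 39.3%.

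**Per-arm interval, only if Wald were used.** For 0/35 it is 0% to 0%, against 0% to 7.2% for Wilson and 0% to 8.2% for Clopper-Pearson. Coverage at n = 35:

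| True rate | 4% | 5% | 6% | 7% | 8% | 10% |
|---|---|---|---|---|---|---|
| Wald | 74.8% | 82.7% | 86.8% | 91.1% | 76.2% | 85.8% |

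At 6%, Wilson covers 94.4% and Clopper-Pearson 98.3%.

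**The case against.** The strongest reply is that the shortfall in the interval the code actually requests is small, and that robust intervals are already planned. Both parts stand. At the planned rates Wald misses nominal by 1.4 points, and at the protocol's rates by about 1 point or less. Miettinen-Nurminen, a score method, covers 88.7% at 26% / 6%, so the gap is not peculiar to Wald. The exact intervals of section 14.4.1 will be reported whatever the data show, so the question is which interval is primary. The larger losses arise at rates that neither document assumes. At 15% / 2% the excess error is in the upper limit; the lower-limit error, which bears on superiority, is 3.8% for both Wald and Newcombe. The decision rests on Hochberg-adjusted p-values ("By using the Hochberg incremental procedure, the type I error for the primary endpoint is controlled at the level of 0.1 bilaterally"), which the choice of interval does not touch.

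Two stronger readings are tempting and the documents do not support them. A reader might infer that the headline interval shrinks to zero width when placebo has no responders. It does not, because it keeps the active arm's variance; zero width needs no variation in either arm, and both arms at zero has probability below 0.0001 at 26% / 6%. A reader might also infer that the per-arm intervals in section 14.2 are Wald. That is plausible, since the section's method is the normal approximation and section 14.4.1 presents Clopper-Pearson as an addition. But section 14.2 does not say so, and Clopper-Pearson is the only per-arm method the SAP names.

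What survives is that the primary difference interval under-covers slightly, by more if response rates are low, and that the per-arm method is unspecified.

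**Conclusion.** The point holds as a minor improvement. The primary Wald interval for the difference covers 88.6% rather than 90% at the SAP's planning rates, and 87.4% and 85.5% at the two lower pairs of rates assumed for illustration. Newcombe is at 90.4% or above in those three cases. The per-arm method needs naming: if it turned out to be Wald, the placebo interval would have zero width with probability 11.5% at a true 6%, and its coverage would lie between about 75% and 91% at whole-percentage rates from 4% to 10%. These figures assume 35 analysed per arm, independent binomial responses, and withdrawals counted as non-responders. Nothing here questions the hypothesis test, the type I error control or the stated power.

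**What to change.** In SAP section 14.2, make the Newcombe hybrid-score 90% interval the primary interval for each difference: `RISKDIFF(CL=NEWCOMBE)`, run once per active-placebo pair. For each arm's response rate, name Wilson or the Clopper-Pearson interval already planned in section 14.4.1. Leave the test, the Hochberg procedure and the exact sensitivity analysis unchanged.

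The cost is a code option and a sentence of text. Mean width of the difference interval at 26% / 6% rises from 0.272 to 0.282, about 4% (0.282/0.272 = 1.04). Interval and test can also disagree near the boundary. With 3/35 against 0/35 the pooled z is 0.0857/sqrt(0.0429 × 0.9571 × 2/35) = 1.77, above 1.645, while the Newcombe interval is −0.2% to 19.6% (Wald 0.8% to 16.4%). The SAP should state that the Hochberg-adjusted test governs the decision and the interval describes precision.
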